2.3 Patient disposition, demographics and other baseline characteristics

2.3.1 Patient disposition

The eligible subjects in study protocol ACZ885GFR01 have to fulfill inclusion and exclusion criteria. Inclusion and exclusion information will be collected in CRF ACZ885GFR01. Frequency and percentage of patients passing and failing Screening will be presented for all screened patients. Percentage will be computed using the total number of screened patients as denominator.

The total number of patients who were completed the study and discontinued the study (and/or treatment) will be presented by number and percentage along with reason of discontinuation for safety set. Patient identification number and whether they completed the study or discontinued from the study will be listed, along with date of last dose and primary reason for premature discontinuation for safety set. Separate listing of all screened failure patients will also be provided for safety set.

2.3.2 Protocol deviations

The number and percentage of patients with protocol deviations will be tabulated by category and deviation for the safety set. Protocol deviations will be listed with date and study day of occurrence, deviation code and severity code for the safety set.

The number of patients included in safety set will be tabulated for all screened patients by number and percentage. Subject exclusion from analysis sets will be listed for all patients with reasons of exclusion (i.e., both protocol and non-protocol deviation).

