10.4 Publication of study protocol and results

Novartis assures that the key design elements of this protocol will be posted in a publicly accessible database such as clinicaltrials.gov. In addition, upon study completion and finalization of the study report the results of this trial will be either submitted for publication and/or posted in a publicly accessible database of clinical trial results.

11 Protocol adherence

Investigators ascertain they will apply due diligence to avoid protocol deviations. Under no circumstances should the investigator contact Novartis or its agents, if any, monitoring the trial to request approval of a protocol deviation, as requests to approve deviations will not be granted.

This protocol defines the study objectives, the study procedures and the data to be collected on study participants. Under no circumstances should an investigator collect additional data or conduct any additional procedures for any research related purpose involving any investigational drugs.

If the investigator feels a protocol deviation would improve the conduct of the study this must be considered a protocol amendment, and unless such an amendment is agreed upon by Novartis and approved by the IRB/IEC it cannot be implemented. All significant protocol deviations will be recorded and reported in the CSR.

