2.2 Analysis sets

Safety Set: Consists of all patients who received at least one dose of study drug and had at least one post-treatment safety assessment in the study. The statement that a patient had no adverse event (AE) also constitutes a safety assessment.

Analysis set	Population codes that cause subjects to be excluded	Non-PD criteria that cause subjects to be excluded
Safety	1	Did not provide informed consent, No treatment taken

Population code: 0=Include in everything, 1=Exclude from safety set

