5.5 Rule of exclusion criteria of analysis sets

All protocol deviations defined at the start of the study are listed with associated population codes in below table. The list will be updated before CDBL.

Protocol Deviation ID	Protocol Deviation Description	Population code
I01	Written informed consent was not obtained before performing any assessment.	1
M01	Patient took prohibited concomitant medication	0
E01	Pregnant or nursing female patients, where pregnancy is defined as state of a female after conception and until termination of gestation, confirmed by +ve hCG laboratory test or urinary pregnancy test	0
S01	Canakinumab not administered as per protocol dosage different than 2mg/kg or 4 mg/kg	0
S02	Canakinumab not administered per protocol schedule. Difference between the dose on consecutive visits (dd-mmm-yyyy) and (dd-mmm-yyyy) is not between 6 weeks to 8 weeks.	0
	No treatment is taken.	1

6 Reference

Clinical Study Protocol CACZ885G2301E1: An open-label extension study of canakinumab (ACZ885) in patients with Systemic Juvenile Idiopathic Arthritis (SJIA) and active systemic manifestations who participated in studies ACZ885G2301 and ACZ885G2305; and response characterization study in canakinumab treatment-naïve patients with active SJIA with and without fever

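### The protocol-deviation table and listing use the Safety Set, but the consent deviation (I01) removes a patient from that set, so neither output can show it

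*SAP*

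**What the plan says.** SAP 2.3.2 plans two deviation outputs, both on the Safety Set. For the table: "The number and percentage of patients with protocol deviations will be tabulated by category and deviation for the safety set". For the listing: "Protocol deviations will be listed with date and study day of occurrence, deviation code and severity code for the safety set".

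SAP 5.5 lists the deviations with a population code for each. I01 reads "Written informed consent was not obtained before performing any assessment" and has code 1. M01, E01, S01 and S02 have code 0. A last row, for patients who took no treatment, has code 1 but no deviation ID.

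SAP 2.2 gives the meaning of the codes: "Population code: 0=Include in everything, 1=Exclude from safety set". Its table also names two exclusion criteria that are not protocol deviations: "Did not provide informed consent, No treatment taken". The definition in words, however, does not mention consent. It reads: "Consists of all patients who received at least one dose of study drug and had at least one post-treatment safety assessment in the study". Protocol 9.1 defines the set in the same way.

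SAP 2.3.2 plans two further outputs on wider populations. Safety Set membership is tabulated over all screened patients, and exclusions are listed for everyone: "Subject exclusion from analysis sets will be listed for all patients with reasons of exclusion (i.e., both protocol and non-protocol deviation".

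Protocol section 11 commits the sponsor as follows: "All significant protocol deviations will be recorded and reported in the CSR".

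**The concern.** A deviation table should count deviations in everyone who could have had one. Here the deviation being counted also removes the patient from the population in which it is counted. I01 is the only numbered deviation that the SAP treats as grounds for exclusion, and it is the only one that the table and listing cannot show.

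Consent timing is a practical matter in this design. The last visit of the parent study is also the first visit of this one (Protocol 3.1), and consent must come before any study-related activity (Protocol 4.1). Protocol 8.1 requires full verification that consent is present. If monitoring finds a failure, the deviation table has no means of reflecting it.

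The stake is the accuracy of the compliance reporting. A reader who looks only at the deviation table would see no consent deviations, whether or not any occurred. Because SAP 2.2.1 repeats every planned table by pathology, the same gap carries into each subgroup table.

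**Working it through.** The plan states no figure to reproduce, and no sample size or error rate is involved. The check is set logic, followed by an illustration of size.

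**Inputs**

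| Input | Value | Source |
|---|---|---|
| Population of the deviation table | Safety Set | SAP 2.3.2 |
| Population of the deviation listing | Safety Set | SAP 2.3.2 |
| Code for I01 | 1 | SAP 5.5 |
| Code for M01, E01, S01, S02 | 0 | SAP 5.5 |
| Meaning of code 1 | Excluded from the Safety Set | SAP 2.2 |
| Maximum number of patients, N | 40, or 41 | Protocol synopsis; Protocol section 4 |
| Number with I01, k | Not given; 1 to 3 assumed | Assumption |

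**Step 1: I01 itself.** Let D be the patients with I01 and S the Safety Set. Code 1 removes every member of D from S, so D ∩ S is empty. The table counts the members of D ∩ S, which is 0 for every k. The listing has no I01 entry for the same reason.

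**Step 2: other deviations in the same patient.** Let X be the patients with a code 0 deviation such as M01. The table counts X ∩ S. A patient in both X and D is outside S, so that patient's M01 is lost as well. Code 0 deviations in patients without a code 1 exclusion are unaffected.

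**Step 3: illustration of size.** The true share is k/N; the plan's table would give 0/(N − k). This assumes that all N patients are screened and that none leaves the Safety Set for another reason.

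| k (assumed) | True share, N = 40 | Plan's table | True share, N = 41 | Plan's table |
|---|---|---|---|---|
| 1 | 1/40 = 2.5% | 0/39 | 1/41 = 2.4% | 0/40 |
| 2 | 2/40 = 5.0% | 0/38 | 2/41 = 4.9% | 0/39 |
| 3 | 3/40 = 7.5% | 0/37 | 3/41 = 7.3% | 0/38 |

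**Step 4: dependence on the code.** If the definition in words governed alone, a patient with I01 who was dosed and then assessed would stay in S and would be counted. One who was never dosed, or never assessed after dosing, would still be missing. Step 1 therefore holds in full when code 1 is applied, as SAP 5.5 and 2.2 direct, and holds in part otherwise.

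**The case against.** The strongest answer is that SAP 2.3.2 already covers these cases. The exclusion listing is for all patients and gives reasons, including protocol deviations, so every patient removed for I01 appears in the report. This stands, and it limits the point. A reader might infer that the plan contradicts Protocol section 11, or that the report would make a false statement of compliance. The documents do not support either. Section 11 asks that significant deviations be recorded and reported; it prescribes no table or denominator, and the exclusion listing reports them. What the listing does not do is correct the table, and it is not specified to give date, study day or severity code.

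A reader might also extend the point to the row for patients who took no treatment, since it too has code 1. That goes too far. SAP 2.2 names it among the criteria that are not protocol deviations, and SAP 5.5 gives it no deviation ID, so its absence from a deviation table is not a fault.

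A third objection is that no table shell is shown, so an empty category may be omitted and not printed as a zero. This is fair: the documents establish that I01 cannot be counted, and do not establish how the empty row would look.

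Finally, SAP 5.5 says that the deviation list will be updated before database lock. That concerns the list. It does not promise a change to the population in SAP 2.3.2, and the current text gives I01 code 1.

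**Conclusion.** The point holds for I01 and for the two outputs named. Followed as written, the deviation table and the deviation listing cannot show a consent deviation, or any other deviation in the same patient, whatever the true number. The conclusion rests on applying population code 1 as SAP 5.5 and 2.2 state. The figures of about 2.4% to 7.5% rest on an assumed 1 to 3 cases out of 40 or 41 and are illustrative only.

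The impact is minor. This is a descriptive single-arm study, the cases still reach the report through the exclusion listing, and no adverse event rate or conclusion changes with the population used for the deviation outputs. It is nevertheless a stated rule that gives a wrong count, and it is easy to correct.

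**What to change.** In SAP 2.3.2, produce the deviation table and the deviation listing for all screened patients instead of the Safety Set. The section already uses that population for the Safety Set membership table, so no new analysis set is needed. Leave the population of every other output as it is; disposition, demographics, exposure, adverse events and deaths need no change for this reason.

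Two details should be settled with it. SAP 2.1.1 counts study day from the start of study drug, so the listing should leave study day blank for a patient who was never dosed. And SAP 2.2 should reconcile the worded Safety Set definition with the code 1 rule, stating whether a patient who was dosed and assessed but has I01 is in or out. The population change works whichever way that is decided.

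The cost is one line of wording and a population flag for one table and one listing, carried through to the table's repeats by pathology, plus a sentence in SAP 2.2. No new data are needed.

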2.3.3 Background and demographic characteristics

Demographics data (except sex and age) and baseline characteristics are collected from the CACZ885G2301E1, CACZ885N2301 or CACZ885G2306 study. Sex and date of birth will be re-collected in the CRF. The following demographic characteristics collected in the CRF at screening will be summarized using the Safety set.

Continuous variables:

- Age (years)

Categorical variables:

- Age group (years) (≥ 2 - <4, ≥ 4 - <6, ≥ 6 - <12, ≥ 12 - <20)
- Sex (Male, Female)
- Race (Caucasian, Black, Asian, Native American, Pacific Islander, Other)

The following baseline disease characteristics will be summarized using the Safety set.

- Steroid (oral) free at baseline(Yes, No)
- Median dose of steroid
- MTX free at baseline(Yes, No)
- C-reactive protein (mg/L)

The below information will be included for (SJIA)

- Number of active joints
- Number active joints(≤ 26 , >26)
- Number of joints with limitation of motion

2.3.4 Medical history and current medical condition

Medical history will be coded using the Medical Dictionary for Regulatory Activities terminology (MedDRA version 18.1 and above). History/conditions will be summarized for the safety set by primary system organ class and preferred term. Verbatim recorded history/conditions will be listed together with the coded terms, date of diagnosis/surgery and whether the problem was ongoing at start of the study ACZ885FR01.

All medical history data will be taken from the the CACZ885G2301E1, CACZ885N2301 or CACZ885G2306 study.

2.4 Treatments (study treatment, rescue medication, concomitant therapies, compliance)

2.4.1 Study treatment / compliance

The maximal total single dose of canakinumab (ACZ885) allowed is 300 mg, which is administered as two subcutaneous 150 mg injections once every 4 weeks.

The canakinumab dose interval (i.e. every 6, 8 or 12 weeks) may also be prolonged in patients with adequate response according to the clinical response and investigators judgment.

The extent of exposure will be examined to determine the degree to which safety can be assessed for canakinumab (ACZ885). The extent of exposure to study drug will be characterized according to the duration of exposure and the number of patients exposed.

Duration of exposure to the treatment will be calculated as the number of days between the first dose date and the last dose date exposed to that treatment over the specified period in Ilaris (ACZ885GRR01) study, expressed as: Duration of exposure = ((Date of last known dose of study drug – Date of first dose of study drug) – Number of days interrupted) + 1.

The duration of exposure (in days) and the cumulative volume administered (in mL) will be summarized with descriptive statistics (n, mean, median, standard deviation, minimum, maximum, Q1, Q3) for the safety set.

The total number of doses (injections) administered, number of 2 mg/kg doses administered, number of 4 mg/kg doses administered will be summarized with number and percentage for overall, 2mg/kg and 4 mg/kg dose group for safety set. By subject listing along with dose date will be provided for safety set.

The duration of exposure (in days) and number of injection will be summarized for the safety set as

- a continuous variable with the standard descriptive statistics
- a categorical variable for number of does (injections) administered classified into 1-4, 5-8, 9-12, 13-16, 17-20, 21-24 with number and percentage for below group.
 - Number of doses (injections) administered
 - Number of 1 mg/kg q4w doses administered
 - Number of 2 mg/kg q4w doses administered
 - Number of 4 mg/kg q4w doses administered
 - Number of 2 mg/kg q8w doses administered
 - Number of 4 mg/kg q12w doses administered
 - Other dose administered
 - No dose administered
- Number of subject and percentage at baseline, reduction in dose at end of study, increase in dose at end of study and stable dose with all dose amount.

- a continuous variable total cumulative volume injected with the standard descriptive statistics.

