1.1 Background

Systemic Juvenile Idiopathic Arthritis (SJIA) is a subset of Juvenile Idiopathic Arthritis (JIA), a serious and potentially disabling form of arthritis that occurs in children 16 years of age and younger, and accounts for approximately 4 - 17 % of JIA (Quartier 2007, Ravelli and Martini 2007). In contrast to other JIA subtypes SJIA is associated with systemic symptoms such as fever, rash, anemia, leukocytosis, elevated erythrocyte sedimentation rate and acute-phase. The peak age of disease onset lies between 18 months and 2 years, but SJIA may occur in children of any age and, rarely, in young adults too (Woo 2006).

Several lines of evidence show that interleukin-1 (IL-1) plays a pivotal role in the pathogenesis of SJIA (Dinarello 2005, Pascual et al 2005).

Ilaris[®] (Canakinumab) is a human monoclonal anti-human interleukin-1 beta (IL-1 beta) antibody of the IgG1/ κ isotype. Canakinumab binds with high affinity specifically to human IL-1 beta and neutralizes the biological activity of human IL-1 beta by blocking its interaction with IL-1 receptors, thereby preventing IL-1 beta-induced gene activation and the production of inflammatory mediators. Canakinumab has a half-life of approximately 21-28 days.

To date, four clinical studies (CACZ885A2203, CACZ885G2305, CACZ885G2301, and CACZ885G2301E1) have been performed by Novartis to evaluate canakinumab as a treatment for patients with SJIA.

Ilaris[®] received Marketing Authorization by the EMA for patients with Systemic Juvenile Idiopathic Arthritis (SJIA) on August 2013 for *the treatment of active Systemic Juvenile Idiopathic Arthritis (SJIA) in patients aged 2 years and older who have responded inadequately to previous therapy with non-steroidal anti-inflammatory drugs (NSAIDs) and systemic corticosteroids. Ilaris[®] can be given as monotherapy or in combination with methotrexate.*

Study CACZ885G2301E1 is a Phase III study designed to assess long-term safety and efficacy data for patients with SJIA who either participated in the CACZ885G2305 and CACZ885G2301 registration studies or were treatment-naïve to canakinumab. In France, 48 patients were enrolled in the CACZ885G2301E1 study at four centers (Necker, Kremlin- Bicêtre, Lyon, and Strasbourg). Study CACZ885G2301E1 is ending on November 2014 and 3 sites (Necker, Kremlin-Bicêtre, and Lyon) still have patients under treatment.

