Dose adjustments (for all patients):

Patients may receive an up-titration or may resume canakinumab if they re-flare (maximum dose of 300 mg (or 4 mg/kg s.c for patients ≤ 40 kg q4w).

The canakinumab dose interval (i.e. every 6, 8 or 12 weeks) may also be prolonged in patients with adequate response according to investigators judgment.

Every patient withdrawn from CACZ885GFR01 study due to a remission will be allowed to resume canakinumab in case of relapse and will be followed up again in the study.

Canakinumab will be administered at the study center.

End of treatment

For patients treated for SJIA:

Investigators will be informed as soon as this indication is commercially available in order to organize at the next planned visit the dropout of the patients. If no visit is planned within 2 months of notification reception, the investigators will have to contact the patient in order to organize patient's study termination. Investigators will have the possibility to perform a last canakinumab administration during the last visit of the protocol.

For patients treated for TRAPS, HIDS and crFMF:

Investigators will be informed as soon as this indication is commercially available in order to organize at the next planned visit the dropout of the patients. If no visit is planned within 2 months of notification reception, the investigators will have to contact the patient in order to organize patient's study termination. Investigators will have the possibility to perform a last canakinumab administration during the last visit of the protocol.

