5.5.11 Early study termination

The study can be terminated at any time for any reason by Novartis. Should this be necessary, the patient should be seen as soon as possible and treated for a prematurely withdrawn patient. The investigator may be informed of additional procedures to be followed in order to ensure that adequate consideration is given to the protection of the patient's interests.

6 Visit schedule and assessments

Visits will take place at the patient's scheduled drug administration date (approximately every 4 weeks or less frequently according to investigators judgment i.e. 6, 8 or 12 weeks).

If no administration is performed within the 12 weeks of previous injection, a control visit will be performed at Week 13 +/- 7 days after the last administration in order to evaluate safety and need for the patient to continue the treatment and the study.

Table : scheduled visits and evaluations

Visits	Inclusion ⁽¹⁾	Visits for canakinumab administration ⁽⁴⁾	End of the study visit ⁽²⁾
Visit window (days)	+/- 7	+/- 7	+/- 7
Inclusion/ exclusion criteria	X		
Written informed consent	X		
Demographic data	X		
Treatment administration	X	X	X
Concomitant treatment	X ⁽³⁾	X	X
Adverse events		X	X
End of the study			X

- 1) The date of last visit of CACZ885G2301E1/CACZ885N2301/CACZ885G2306 study will be the first visit of this extension study.
- 2) The end of study is defined as premature termination or end of the study according to protocol: in the month following the availability of repaid product in France.
- 3) Corticosteroids and methotrexate only.
- 4) Visits will take place at scheduled administration date every 4, 6, 8 or 12 weeks (section 5). Dose interval may be prolonged during the study (i.e. visits every 6, 8 or 12 weeks or longer in case of adequate response at the discretion of the investigator (section 5). If no administration is performed within the 12 weeks of previous injection, a control visit will be performed at Week 13 +/- 7 days after the last administration in order to evaluate safety and need for the patient to continue the treatment and the study.

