9.3 Treatments

The exposure to study drug (number of injections) and duration of exposure (days) will be summarized and listed by dose.

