2.1.1 General definitions

Study treatment: refers to: Ilaris = ACZ885

Study treatment start and end date: Study treatment start date is defined as the first date of study drug is administered and recorded on the Study Medication Dosing Record in CRF page. Similarly, study drug end date is defined as the last date of study drug is administered.

Study day: Study day will be calculated as (event date – study drug start date + 1 day) for events that occurred on or after study drug start date (e.g. visit, adverse events). For events prior to study drug start date (e.g., time of diagnosis), study day will be negative and calculated as (event date – study drug start date).

Baseline and post baseline: In general, a *baseline* value refers to the last measurement made prior to administration of the first dose of study treatment or the average values taken prior to administration of the first dose of study treatment. A post-baseline value refers to a measurement taken after the first dose of study treatment.

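### Duration of exposure stops on the day of the last injection, so observed on-drug time is dropped for patients who leave without a final-visit dose, reach the Week 13 control visit, or interrupt treatment

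*SAP*

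**What the plan says.** SAP 2.4.1 bases duration of exposure on "Date of last known dose of study drug – Date of first dose of study drug) – Number of days interrupted) + 1". SAP 2.1.1 is consistent with this: "study drug end date is defined as the last date of study drug is administered". Neither section adds any time after the last injection, and neither says when an interruption begins.

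The protocol supplies no formula. Its section 9.3 asks only that "duration of exposure (days) will be summarized and listed by dose". On the drug and its schedule it states:

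- Section 1.1: "Canakinumab has a half-life of approximately 21-28 days".
- Section 6, visit table, footnote 4: "Visits will take place at scheduled administration date every 4, 6, 8 or 12 weeks (section 5").
- Section 6, text and the same footnote, counting from the most recent injection: "If no administration is performed within the 12 weeks of previous injection, a control visit will be performed at Week 13 +/- 7 days".
- Section 5, End of treatment: "Investigators will have the possibility to perform a last canakinumab administration during the last visit of the protocol". The visit table also marks treatment administration at the end of study visit.

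SAP 2.4.1 gives the purpose of the summary: "The extent of exposure will be examined to determine the degree to which safety can be assessed for canakinumab (ACZ885").

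**The concern.** Last date minus first date plus 1 is a natural count for a daily drug. Here one injection is meant to serve 28 to 84 days, and the formula credits the final one with 1 day. A patient with a single injection has 1 day of exposure under every regimen.

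The SAP treats the days after the last dose as on-drug elsewhere: SAP 2.8.1 counts non-serious events for 7 days and serious events for 30 days after the last dose, and SAP 2.8.2 summarises deaths to 30 days. The protocol also schedules safety observation in that period through the Week 13 control visit. At stake is the table the SAP uses to judge how far safety can be assessed. It would be biased low, and by different amounts for patients followed equally long on different intervals.

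**Working it through.** The documents state no exposure total, so there is no figure to reproduce. I applied the SAP formula directly.

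**Inputs.** Intervals I = 28, 42, 56 or 84 days (Protocol section 6); half-life 21-28 days (Protocol 1.1). My assumptions: a constant interval, no interruption, and follow-up of 168, 336 or 672 days with no dose at the last visit.

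**Formulas.** For k injections at interval I:

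- SAP duration = (k − 1) × I + 1
- Days through the end of the last interval = k × I
- Days not counted = I − 1 = 27, 41, 55 or 83

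**Equal follow-up of 336 days**

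| Interval | k | SAP duration | Not counted | Share of 336 |
|---|---|---|---|---|
| q4w | 12 | 11 × 28 + 1 = 309 | 27 | 8.0% |
| q6w | 8 | 7 × 42 + 1 = 295 | 41 | 12.2% |
| q8w | 6 | 5 × 56 + 1 = 281 | 55 | 16.4% |
| q12w | 4 | 3 × 84 + 1 = 253 | 83 | 24.7% |

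In the same order, the shares are 16.1%, 24.4%, 32.7% and 49.4% at 168 days, and 4.0%, 6.1%, 8.2% and 12.4% at 672 days.

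**Equal number of injections.** With 12 injections, q4w loses 27 of 336 days (8.0%) and q12w loses 83 of 1,008 (8.2%). The difference between regimens is then in days, not in percentage.

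**Dose at the last visit.** If the last injection falls on the last visit, day L, then the earlier of L + I − 1 and L is L. That is the SAP value, so no observed time is lost.

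**Week 13 control visit.** This falls at 91 ± 7 days, that is, 84 to 98 days after the last injection. All of the uncounted 27 to 83 days then lie inside observed follow-up.

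**Interruptions.** Suppose the gap between two injections is g days. Counting interrupted days from the day after the earlier injection removes g − 1 days. Counting from the date the next dose was due removes g − I. The difference is again I − 1 days per interruption, and the SAP does not say which count applies.

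**Split by dose.** Six q4w injections followed by two q12w injections span 6 × 28 + 2 × 84 = 336 days. The formula applied to the whole gives 168 + 84 + 1 = 253. Applied to each segment it gives (5 × 28 + 1) + (84 + 1) = 141 + 85 = 226.

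**Drug remaining**, as 0.5^(days / half-life): 40-50% at 4 weeks, 25-35% at 6, 16-25% at 8, and 6-12.5% at 12.

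**The case against.** The strongest reply is that no safety result depends on this number. Adverse events are reported as counts and percentages of patients, the analysis is descriptive, and no patient-time denominator is planned. The SAP also summarises number of injections, injections by regimen and cumulative volume, and lists dose dates by subject. This stands, and it limits the matter to the exposure summary.

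Second, a patient injected at the final visit loses no observed time, and a rule that always added a full interval would credit time after routine event collection has ended. This also stands, so any correction has to be capped at the last study visit.

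Third, an interval rule is a convention. The same 4 mg/kg injection would earn 28 days under q4w and 84 under q12w, with little drug left by day 84. That is fair, but the rule gives regimens with equal follow-up equal exposure, which the SAP formula does not.

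Fourth, the documents record injection date and volume (Protocol 6.2) and dosages and dose changes (Protocol 5.5.4 and 5.5.5), but do not say that the planned next interval is recorded. Footnote 4 also allows longer intervals. A fallback rule is therefore needed.

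Fifth, correcting exposure alone leaves the 7-day non-serious window as it is. At full intervals, exposure would run 27 − 7 = 20 to 83 − 7 = 76 days beyond it. This should be stated in the report.

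**Conclusion.** The point holds for patients who leave without a final-visit dose, are followed to the Week 13 control visit, or interrupt treatment. For them the formula drops up to 27, 41, 55 or 83 days of observed on-drug time after an injection. Over an assumed 336 days the shortfall is 8% to 25%, depending on interval. The percentages rest on the assumed follow-up and constant intervals, and they shrink as follow-up lengthens.

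The documents do not support three stronger readings:

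- A reader might multiply by the 41 patients of Protocol section 4: 41 × 27 = 1,107 days to 41 × 83 = 3,403 days, or about 3.0 to 9.3 patient-years. That is uncounted dosing cover, not lost observation. It assumes that every patient loses a full interval, and its upper end puts all of them on q12w.
- A reader might infer that adverse event results are biased. The planned percentages do not use exposure time.
- A reader might infer a further loss at each regimen change. The SAP does not define duration by regimen segment; the loss arises only if the by-dose table of Protocol 9.3 is built by applying the formula to each segment.

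The change is worth making before database lock. It corrects a descriptive table and no inference depends on it.

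**What to change.** Amend SAP 2.4.1, and 2.1.1 to match:

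- End of exposure is the earliest of last dose date + assigned interval − 1 day, last study visit, and death.
- Take the interval from the dosing record. Where the next interval is not recorded, use the last interval in use and flag the patient.
- Count interrupted days only from the date the next dose was due.
- If duration is tabulated by dose (Protocol 9.3), end each segment the day before the first dose of the next regimen, or at that segment's last dose + interval − 1 day if earlier.
- Keep the first-to-last-dose figure as a labelled footnote.
- State that the 7-day window for non-serious events in SAP 2.8.1 is shorter than this exposure period.

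The cost is SAP wording and one derivation. Injection dates and dose changes are already recorded, and the fallback covers an unrecorded interval. The small downside is that the figures will not match summaries using the first-to-last-dose convention; the footnote deals with that.
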